### **3.3.9 Concomitant Therapy**

Participants should not be actively engaged in other forms of addiction treatment during the treatment phase of the study. Ongoing counseling or therapy for conditions other than substance use disorders is permitted. Most psychotropic medications are excluded until after the double-blind drug administration sessions. Excluded medications include antidepressants, antipsychotics, psychostimulants, pharmacologic treatments for addictions, other dopaminergic or serotonergic agents, lithium, and anticonvulsants. Other concomitant medications will be reviewed during the screening medical assessment, and a study physician-investigator will determine whether the participant should continue the medication, temporarily discontinue it, or be excluded from the study. If excluded medication is started or resumed during the double-blind follow-up period (i.e.,

during weeks 9-38) and the participant is interested in completing in the open-label session, the study physician will consider whether it is clinically appropriate to taper the medication in preparation for the open-label session, consulting with the participant's prescriber as needed. Examples of possibly appropriate situations include psychostimulant treatment of ADHD or antidepressants for mild depression or anxiety disorder. If the risks of a taper are deemed acceptable and the participant agrees, the medications may be tapered by the participant's prescriber as clinically appropriate. The excluded medications must be completely discontinued for 5 half-lives or one week, whichever is greater, prior to the open-label medication session.

### 3.3.10 Measures

Measures are listed in Table 1 below, organized by domain.

Table 1. Assessment Schedule		Scr.	BL	W04	W05	W08	W09	W12	W24	W36	W38	W39	W42	W54
Medical evaluation	History and physical, liver function tests, complete blood count, Chem 7, U/A, serum pregnancy test, height and weight, medical history intake form	550'												
	ECG		5'							5'				
	Concomitant meds, menstrual calendar		5'	5'	5'	5'	5'	5'	5'	5'	5'	5'	5'	5'
	Urine pregnancy test				5'		5'				5'			
Psychiatric and SUD assessment	Structured Clinical Interview for DSM-IV (SCID), Family History Questionnaire, Folstein MMSE	75'												
Other baseline characteristics	Attentional Resource Allocation Scale, Treatment Goal Form, Demographics Form, Locator Form			15'										
Withdrawal	CIWA-Ar	5'		5'		5'					5'			
Substance use and consequences	Time-line Follow-back, BAC	30'	10'	10'		10'		10'	10'	10'	10'		10'	10'
	Hair/ Nail sample for ethyl glucuronide									5'				
	Urine Drug Screen	5'		5'		5'		5'	5'	5'	5'		5'	5'
	Short Inventory of Problems (past 3 months)		5'					5'	5'	5'				5'
Acute Hallucinogen Effects	5D-ASC, HRS, SCQ, Monitor Rating Scale, Mysticism scale, guesses of medication received, MUSE questionnaire			30'		30'					30'			
Persisting Effects	Mysticism Scale (lifetime), Spiritual Transcendence Scale, Persisting Effects Questionnaire (follow-up)		90'							90'				90'

	only), BMMRS, NEO-PI-3, Schwartz Value Survey													
Motivation	Readiness rulers		5'	5'	5'	5'	5'	5'	5'	5'	5'	5'	5'	
Self-efficacy	Alcohol Abstinence Self-efficacy Scale		10'	10'	10'	10'	10'	10'	10'	10'	10'	10'	10'	
Craving	Penn Alcohol Craving Scale		5'	5'	5'	5'	5'	5'	5'	5'	5'	5'	5'	
Self-Compassion	Self-Compassion Scale (Short Form)		5	5	5	5	5	5	5	5	5	5	5	
Mood/ Anxiety	Ham-D, Ham-A		20'	20'	20'	20'	20'	20'	20'	20'	20'	20'	20'	
	Adverse Events Case Report Form			5'	5'	5'	5'	5'	5'	5'	5'	5'	5'	
Safety	Vital Signs and weight	5'	5'	5'	5'	5'	5'	5"	5'	5'	5'	5'	5'	
	Visual Analog Scales for abuse potential							5'	5'	5'			5'	
Tx satisfact.	Visual Analog Scales							5'					5'	
Assessment Length		185'	175'	110'	55'	110'	55'	85'	85'	170'	110'	55'	75'	170'

### 3.3.10.1 Medical Evaluation

Medical screening will consist of medical history and physical, ECG, liver function tests, complete blood count, Chem 7, U/A, serum pregnancy test, height, and weight. Labs may be repeated if needed to ensure safety. Concomitant medications will be recorded at screening and updated at each visit. Women of childbearing potential will complete a menstrual calendar at each assessment visit, and urine pregnancy tests will be completed prior to each drug administration session. Vital signs will be measured at each assessment visit, and during the psilocybin sessions (q 30 minutes for 2 hours, then hourly to 6 hours post administration).

### 3.3.10.2 Psychiatric and Substance Use Disorder Assessment

For Axis I diagnoses we will use the Structured Clinical Interview for DSM-IV (SCID), a structured interview which yields DSM-IV diagnoses for Axis I disorders including substance abuse and dependence diagnoses [122]. To allow DSM-5 substance use disorder diagnoses to be made as well, an item will be added for the DSM-5 craving criterion. Excellent inter-rater reliability of the DSM-III-R version of the SCID has been reported for schizophrenia, major depression, and substance use disorders (kappas ranging from 0.85 to 0.96), with adequate to excellent reliability for other mood and anxiety disorders, with the exception of obsessive-compulsive disorder [122]. Family history of addiction and exclusionary psychiatric disorders will be recorded using a Family History Interview. The Folstein Mini-Mental State Examination [111] will be used to screen for cognitive impairment. A score below 26 will exclude subjects from the study.

### 3.3.10.3 Alcohol Withdrawal

The Clinical Institute Withdrawal Scale—Alcohol, revised (CIWA-Ar) [123] will be used to assess alcohol withdrawal at screening and before the psilocybin sessions.

### 3.3.10.4 Substance Use

#### 3.3.10.4.1 Self-report

The Time-line Follow-back (TLFB) [124, 125] procedure will be used to assess drug use behavior at baseline and follow-up visits. The TLFB is a semi-structured interview that provides estimates of the daily quantity, frequency, and pattern of drug use during a specified time period. It uses a calendar prompt and number of other memory aids (e.g., holidays, payday, and other personally relevant dates) to facilitate accurate recall of drug use during the target period. The TLFB has shown adequate to excellent reliability and validity over a wide range of research and clinical contexts [100, 126, 127]. It is estimated that the

TLFB assessment will take 10-30 minutes to complete, depending on the length of the assessment period and the patterns of alcohol and drug use. Non-study treatment and 12-step attendance will also be recorded on the TLFB form.

### ***3.3.10.4.2 Objective Measures of Alcohol and Drug Use***

Hair/ nail analysis for Ethyl glucuronide (HEtG) Hair/nail samples will be obtained at 24 weeks (20 weeks after the first drug administration session). HEtG is a sensitive and specific measure of recent alcohol consumption, with a cut-off of 27 pg/ng detecting heavy drinking ( $\geq 60$ g alcohol/day) at sensitivity of .92 and specificity of .96 [128, 129]. A 3 cm proximal sample of hair (scalp hair if possible) representing a 3-month history of alcohol use will be obtained at week 24 (20 weeks after the first drug administration session). If participants do not have sufficient hair, then fingernails (2 mm from each of 10 fingernails) may be used as an alternative. Samples will be analyzed quantitatively using a liquid chromatography–tandem mass spectrometry (LC-MS/MS) method. Results may be used categorically.

Breath Alcohol Concentration (BAC) will be measured using the Alcosensor III ® or a similar device, which will be calibrated monthly.

Urine Drug Screen (UDS) We will use the Alere™ iCup ® or similar chromatographic immunoassay to test for use of marijuana, cocaine, opiates, and methamphetamine.

### ***3.3.10.5 Substance Use Consequences***

The Short Inventory of Problems (SIP-2R) [101], past 3 month version, will be used to measure consequences of alcohol use. The SIP-2R is a 15-item measure that assesses five domains of alcohol-related consequences: (1) social, (2) intrapersonal, (3) interpersonal, (4) impulse control, and (5) physical. Derived from the 50-item Drinkers Inventory of Consequences (DrInC), the SIP-2R has excellent reliability and validity.

### ***3.3.10.6 Acute and Persisting Hallucinogen Effects***

#### ***3.3.10.6.1 Acute Hallucinogen Effects***

5-Dimensional Altered States of Consciousness Scale (5D-ASC) [130] will be used to quantify acute hallucinogen effects. This scale has 94 items using the visual analog scale format, yielding 5 primary dimensions. The primary dimensions are “oceanic boundlessness,” “anxious ego-disintegration,” “visionary restructuralization,” “acoustic alterations,” and “altered vigilance.”

The Hallucinogen Rating Scale (HRS), developed and validated at the University of New Mexico by Rick Strassman et al. (1994) in studies of intravenous DMT and validated in ayahuasca users [131], will also be administered following each drug administration session. It is being used by the Hopkins and Tucson groups in their psilocybin research, and has been used to assess effects of a wide variety of psychoactive drugs including MDE, methamphetamine, psilocybin, ibogaine, MDMA, ayahuasca, methylphenidate, d-amphetamine, ketamine and mCPP. This 99-item scale has 6 subscales: intensity, somesthesia, affect, perception, cognition, and volition.

The Mysticism Scale will be used to assess “mystical” dimensions of the hallucinogen experience. This 32-item, 3-factor questionnaire has been used in studies of non-drug-induced mystical experiences [132], and has also been used in the psilocybin work of Griffiths et al. (2006).

The States of Consciousness Questionnaire (SCQ) will also be administered. This 100-item questionnaire has been used extensively to measure mystical-type states of consciousness in hallucinogen administration experiments [97, 113, 133-135]. This scale contains the 43 items of the Pahnke-Richards Mystical Experience Questionnaire (MEQ) [97].

A 20-item Monitor Rating Scale [97] will be completed by both therapists at intervals during the psilocybin sessions (every 30 minutes for the first 2 hours, then hourly) to provide objective ratings of participants’ behavior and affect during the session.

A novel Music and Sound Experience (MUSE) questionnaire will be administered at the end of each medication session. The questionnaire contains 20 items that assess the impact the music and sounds played during the medication session had on the quality of the participant's experience.

### **3.3.10.6.2 Persisting Hallucinogen effects**

The Persisting Effects Scale [97] is based in large part on items used by Pahnke (1963; 1969), and includes subscales related to positive and negative changes in attitudes, mood, social functioning, and behavior.

The Mysticism Scale (lifetime version) and the ASPIRES Spiritual Transcendence Scale will also be used as measures of persisting effects. The Spiritual Transcendence Scale is a scale addressing the individual's sense of connectedness and meaning [136]. The scale yields a total score and three empirically derived factor scores: prayer fulfillment, universality, and connectedness. We will use the 13-item short form.

The Brief Multidimensional Measure of Religiousness/Spirituality (BMMRS) [137] will be used as a broad measure of multiple domains of spirituality.

The NEO Personality Inventory 3 (NEO-PI-3) [138] will be used to assess personality at baseline, 12, and 36 weeks as a recently published study has shown that psilocybin administration can cause significant persisting increases in the personality dimension of "openness" [120]. The NEO-PI-3 is an updated version of the NEO-PI-R [139]. The NEO inventories measure the personality dimensions of the 5-factor model: neuroticism, extraversion, openness, agreeableness, and conscientiousness, with 6 "facets" within each factor.

The Schwartz Value Survey [140] will be used to assess participants' values and possible shifts in relation to treatment. This instrument includes 57 items organized into 10 cross-culturally valid dimensions of value: self-direction, stimulation, hedonism, achievement, power, security, conformity, tradition, benevolence, and universalism [141].

### **3.3.10.7 Potential Mediators of Therapeutic Effect**

#### **3.3.10.7.1 Motivation**

Readiness Rulers will be used as to measure motivation in the course of the trial, [142]. This simple measure comprises Likert-scale ratings of the participant's perception of the importance of change in drinking, confidence of ability to change, and readiness for change. Commitment to the goal of abstinence will be added as a fourth item.

#### **3.3.10.7.2 Self-efficacy**

The Alcohol Abstinence Self-Efficacy Scale (AASE) [143] is a self-report questionnaire which has been used widely in the alcohol treatment research, both as a predictor of outcome and as a client-treatment matching variable [144, 145]. Item content of the AASE-C subscale asks the respondent to rate the confidence they have to avoid drinking in different situations. In time-ordered analyses, a relationship has been demonstrated between the AASE-C and AA behaviors and drinking, both at 6 months [146] and 3 years after completing outpatient treatment [147].

#### **3.3.10.7.3 Alcohol craving**

The Penn Alcohol Craving Scale [148] will be used to assess craving. This scale has 5 Likert-scaled items with excellent internal consistency and evidence of predictive, construct, and discriminant validity.

#### **3.3.10.7.4 Self-compassion**

Self-compassion is a construct, derived from Buddhist psychology, which denotes a kind and non-judgmental attitude toward oneself [149]. A reliable and valid 12-item form of the Self-Compassion Scale [150] will be used as measure of self-compassion.

#### **3.3.10.7.5 Mood and Anxiety**

The Hamilton Anxiety (Ham-A) [151] and Depression (Ham-D) (17-item) [152] scales will be used as measures of depression and anxiety at baseline and at each follow-up visit.

### ***3.3.10.7.6 Treatment Satisfaction***

Visual Analog Scales will be used to assess participants overall satisfaction with study treatment (separate scales for satisfaction and usefulness).

### **3.3.10.8 Potential Moderators of Acute and Persistent Effects of Psilocybin**

In addition to the participant characteristics measured above, the following measures will be obtained at baseline.

#### ***3.3.10.8.1 Dissociation and Absorption***

The Attentional Resource Allocation Scale (ARAS) [153] will be used as measure of dissociation and absorption. This questionnaire is derived from factor analyses of two large samples administered both the a composite of the Tellegen Absorption Scale (a 34-item measure of absorption) [154] and the Dissociative Experiences Scale (a 28-item self-report questionnaire) [155] (items of both scales were Likert-scaled in this study). Exploratory and confirmatory factor analyses yielded 15 items loading on three highly intercorrelated factors: imaginative involvement, dissociative amnesia, and attentional dissociation. The single factor model also produced acceptable (but statistically inferior) fit indices.

#### ***3.3.10.8.2 Thoughts About Abstinence***

Using the form that was used in the COMBINE trial [156], participants will be asked to endorse one of seven treatment goals which can be categorized as: 1) total abstinence; 2) conditional abstinence; and 3) moderation.

#### ***3.3.10.8.3 Demographics form***

A standard Demographics form will be used to capture information such as ethnicity, education, and employment.

#### **3.3.10.9 Safety Assessment**

Adverse events (AEs), when present, will be collected on an AE Case Report Form at the end of the psilocybin sessions and at all subsequent visits. The form will include an assessment of clinical significance and study relatedness. Serious Adverse Events (SAEs) will be documented on an additional SAE form. These CRFs will be based on those used in recent NIDA Clinical Trials Network trials. Vital signs will be obtained at each visit and measured frequently during psilocybin sessions: every half hour for the first 2 hours, then hourly for a total of 8 hours, with more frequent readings as needed (See Therapy Manual). To further assess abuse potential, visual analog scales will be used to assess abuse potential. Scales will include desire to use the study medication again, desire to use the study medication again for pleasurable intoxication ("to get high"), and craving for the study medication.

#### **3.3.10.10 Therapist and Participant Guesses of Treatment Assignment**

In order to assess the integrity of the blind, following each drug administration session participants and therapists will be asked to guess 1) what medication was administered (psilocybin or diphenhydramine), and 2) degree of confidence in this guess.

#### **3.3.10.11 Locator form**

A standard locator form will be used to collect information on contact who can help locate participants in case they change address and/or phone numbers. Ideally at least 3 independent contacts will be identified.

### **3.3.11 Data Management and Procedures**

Raw data in case report forms (CRFs) will be reviewed for completeness and accuracy at each visit. CRFs and source documents will be stored in locked cabinets in an office which will be locked when the office is not in use. Identifying data (e.g., consent) will be stored in separate locked cabinets. Data will also be entered into "Research Electronic Data Capture" (REDCap™) hosted at each participating site. At the conclusion of this study de-identified data will be downloaded and the project will be deleted off of REDCap™.

Data will be kept for at least 5 years following completion of the study. No PHI data will be kept unless subjects sign the informed consent form. PHI data of individuals who do not sign an informed consent form will be destroyed. Visits may be conducted in-person or via phone and data will be entered either by direct electronic data capture (e.g., tablet computers) by a research assistant or by the participant, or by independent double entry into an encrypted REDCap™ database located on a server and accessible only to approved staff study through a password-protected computer. The study database will be set up not to accept out-of-range values.

### **3.3.12 Statistical analysis and power**

A full description of the planned analyses for this trial can be found in the Statistical Analysis Plan (SAP)

#### **3.3.12.1 Preliminary analyses**

In addition to the assessment of the distributional properties of key measures at baseline and follow-up, we will evaluate the nature and pattern of missing data and assess treatment group equivalency at baseline on primary substance use measures and patient characteristics that are central to study aims.

*Self-selection and Attrition.* Baseline measures of substance use and other relevant characteristics will be used to compare eligible prospects who do and do not drop out prior to randomization and receiving study medication. Contingent on the scale of measurement of the comparison variable, unprotected t-tests and Chi Squares will be done to compare these groups. Two strategies will be used to examine the impact of post-randomization attrition on study internal validity, and both strategies will employ hierarchical linear modeling (HLM) with binary outcomes depicting attrition status (yes/no) jointly at post-medication session visits (Bernoulli function). First, we will examine attrition by group assignment. Here, the HLM will identify both the main effect of group assignment on later attrition as well as the potential for a group-by-time attrition effect. Second, group equivalency on factors potentially predictive of future drinking will be evaluated with t-tests using baseline drinking intensity and other characteristics as dependent measures.

#### **3.3.12.2 Aim 1 (to characterize the acute effects of PO psilocybin 25 mg/70kg, 30mg/70kg, and 40 mg/kg in alcohol dependent patients)**

##### **3.3.12.2.1 Outcome measures**

The primary safety measures will be changes in vital signs, psychological or other clinically significant adverse events, and serious adverse events using the FDA definition. The primary measure of hallucinogen effect is the 5-Dimensional Altered States of Consciousness Scale (5D-ASC) [130]. Secondary outcomes the Intensity score and other subscales from the Hallucinogen Rating Scale (HRS) [157], the Mysticism scale [132], the Mystical Experience Questionnaire [97], abuse potential visual analog scales, and within-session Monitor Rating Scale Scores.

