The total duration of psychosocial treatment in the double-blind period will be 12 weeks, and double-blind drug administration sessions will occur after 4 and 8 weeks. In the first psilocybin session, a dose of 25 mg/70 kg will be administered. Depending on the response in the first session, the dose for the second session may be increased to 30 mg/70 kg or 40 mg/70 kg, or held at 25mg/70kg. The dose of diphenhydramine will start at 50 mg, and may be increased to 100 mg or held at 50 mg in the second session, depending on response in the first session. Following completion of the double-blind period (34 weeks after randomization) all participants who meet interim safety criteria will be offered an additional session in which psilocybin will be administered. The drug will be administered during 8-hour sessions in an outpatient setting under close medical and psychiatric monitoring. The drug administration sessions will occur in the context of an extended version of Motivational Enhancement Therapy (Motivational Enhancement and Taking Action, META) with the addition of standardized preparation before and debriefing and follow-up after the psilocybin administration sessions. Extensive screening and baseline assessment will be completed, including thorough safety screening and assessment of participant characteristics that could potentially moderate treatment response. Within-session and short-term persisting effects will be assessed. Drinking outcomes and changes in several potential mediators of treatment effect, including motivation, self-efficacy, craving, depression, anxiety, and spiritual dimensions of the experience, will be measured until 50 weeks after the first drug administration session, for a total of 54 weeks from the initiation of treatment.

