
**Aim 1:** To characterize the acute effects of PO psilocybin 25 mg/70 kg, 30 mg/70 kg, and 40 mg/70 kg in alcohol dependent patients: Hypothesis 1: The drug will be well-tolerated, and acute effects will be similar to those observed in normal volunteers.

**Aim 2:** To evaluate the effect of psilocybin treatment on drinking outcomes for 32 weeks after the first administration, relative to diphenhydramine control. Hypothesis 2: A greater decrease in percent heavy drinking days will be observed among participants receiving psychoactive doses of psilocybin in combination with psychosocial treatment than in those receiving diphenhydramine.

**Aim 3:** To test whether or not characteristics of the drug administration session experiences mediate effects of psilocybin on short term (1 week) persisting effects and post-session drinking behavior. Hypothesis 3: Intensity of experience during the drug administration sessions will predict post-session changes in craving, self-efficacy, and motivation, and these changes will in turn predict changes in drinking behavior during the 32 weeks following initial drug administration.

**Aim 4:** To evaluate the explanatory value of changes in alcohol craving, self-efficacy, motivation, and other psychological domains in accounting for the observed experimental effect of psilocybin relative to diphenhydramine control. Hypothesis 4: Changes in craving, self-efficacy, and motivation will mediate the effects of psilocybin treatment on drinking behavior.

**Aim 5:** To evaluate pre-post changes in drinking in participants after they receive psilocybin in the third session. Hypothesis 5: participants in the control group will show decreases in drinking during the 16 weeks following the psilocybin session at week 38.

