To maximize the probability that participants treated with psilocybin will have strong and meaningful experiences while minimizing the chance of significant psychological distress or other adverse events, we propose to titrate the dose of study medications in the second session based on the response in the first session. In the first session, participants in the psilocybin group will receive a moderately high dose of 25 mg/70 kg. For the second session, the dose will be titrated within a range of 25-40 mg/70 kg, depending on the participant’s response in the prior session. The dose will be increased if the participant tolerated the 25 mg/70kg dose well (no clinically significant adverse psychiatric or medical effects) and is willing to increase the dose. The dose will be increased to 30 mg/70kg if the participant had reported strong subjective response to the first session, as evidenced by a total score on the MEQ  $\geq 0.6$ . The dose will be increased to 40 mg/70 kg only if the participant a) had a relatively mild response to 25 mg/70 kg (MEQ total score  $< 0.6$ ) and b) the therapists and participant agree that increasing the dose to 40mg/70kg will be safe and will maximize likelihood of clinical benefit. The dose may be held at 25 mg/70 kg if the participant is not willing to increase the dose. The second session will be canceled if the participant is not willing to undergo a second session, or if he or she experienced clinically significant adverse psychiatric or medical adverse

events related to the first session. Figure 4 illustrates the dosing algorithm. The first and second decision points (whether to conduct the second session and whether to increase the dose) will be determined by the study clinicians in collaboration with the participant. The third decision point (how much to increase the dose) will be determined by the total score of the Mystical Experience Questionnaire (MEQ), scored by a trained research staff member not participating in the study treatment.

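### The abuse-potential scales are an Aim 1 outcome but are first scheduled at week 12, after both double-blind sessions, so no early reading is taken

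*Combined protocol and SAP*

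**What the plan says.** Section 2 states Aim 1 as: "To characterize the acute effects of PO psilocybin 25 mg/70 kg, 30 mg/70 kg, and 40 mg/70 kg in alcohol dependent patients". Section 3.3.12.2.1 lists the secondary outcomes for that aim, and the list ends with "abuse potential visual analog scales, and within-session Monitor Rating Scale Scores".

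Section 3.3.10.9 describes the content of the scales: "Scales will include desire to use the study medication again, desire to use the study medication again for pleasurable intoxication", and craving for the study medication. It names no visit, so the timing comes from Table 1 alone. There, the row "Visual Analog Scales for abuse potential" sits in the Safety block. Its first entry is at week 12, followed by weeks 24 and 36 and one visit after the open-label session.

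The Protocol Abstract says that "double-blind drug administration sessions will occur after 4 and 8 weeks". Section 3.3.8.1.3 sets the doses: "In the first session, participants in the psilocybin group will receive a moderately high dose of 25 mg/70 kg". It continues: "For the second session, the dose will be titrated within a range of 25-40 mg/70 kg, depending on the participant’s response in the prior session". Section 3.3.12.2.2 compares scale scores between randomised groups with t-tests. It names no time point and plans no analysis by dose.

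**The concern.** The stated role of the scales and their schedule do not match. The other subjective and observer scales listed for Aim 1 (5D-ASC, HRS, Mysticism Scale, MEQ within the SCQ, Monitor Rating Scale) are all in the Acute Hallucinogen Effects row of Table 1, completed at each session visit (weeks 4, 8 and 38). The abuse-potential scales are the exception: they have no reading at a session visit or at a one-week visit.

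Section 4.1.3.1.1 acknowledges a theoretical risk that a participant could come to misuse psilocybin after the trial experience. If desire or craving appeared soon after the first session and faded by week 12, these scales would not show it. Week 5 is the one point at which each arm has had a single session at one planned starting dose level, and the scales are not given then.

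**Working it through.** **Timing.** The inputs are sessions at weeks 4 and 8 (Abstract), the open-label session at week 38 (Section 3.3.1), and the first scale entry at week 12 (Table 1).

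- First session to first rating: 12 − 4 = 8 weeks.
- Second session to first rating: 12 − 8 = 4 weeks.
- Third session to the next rating: 42 − 38 = 4 weeks if the last entry is week 42, or 54 − 38 = 16 weeks if it is week 54.
- Ratings at one-week visits (weeks 5, 9, 39): 0 of 3. Ratings at session visits (weeks 4, 8, 38): 0 of 3.

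**Is the week-12 start only an artefact of how the table was read?** Table 1 prints a total length for each visit, so the minutes can be summed without the abuse-potential scales and compared with that total. The items common to these visits are readiness rulers 5, AASE 10, PACS 5, Hamilton scales 20, adverse events 5 and vital signs 5, which sum to 50.

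| Visit | Items other than the visual analog scales and the hair or nail sample | Sum | Printed | Left over |
|---|---|---|---|---|
| Weeks 5, 9, 39 | medications 5 + common 50 | 55 | 55 | 0 |
| Weeks 4, 8, 38 | medications 5 + pregnancy test 5 + CIWA-Ar 5 + TLFB 10 + urine screen 5 + acute effects 30 + common 50 | 110 | 110 | 0 |
| Week 12 | medications 5 + TLFB 10 + urine screen 5 + SIP 5 + common 50 | 75 | 85 | 10 |
| Week 24 | as week 12 | 75 | 85 | 10 |
| Week 36 | as week 12, + persisting effects 90 | 165 | 170 | 5 |
| Week 42 | medications 5 + TLFB 10 + urine screen 5 + common 50 | 70 | 75 | 5 |
| Week 54 | as week 36 | 165 | 170 | 5 |

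The 10 minutes left at week 12 match the abuse-potential scales (5) plus the treatment-satisfaction scales (5). The 10 left at week 24 match the abuse-potential scales (5) plus the hair or nail sample (5). At the session and one-week visits nothing is left.

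**Limits of this check.** The printed totals reproduce only if the 5-minute Self-Compassion Scale and the week-36 ECG are left uncounted. The pregnancy test is placed at the session visits, as Section 3.3.10.1 requires. The 15-minute baseline-characteristics row is placed at baseline, as Section 3.3.10.8 indicates. The hair or nail sample is placed at week 24, as Section 3.3.10.4.2 states. Because the totals omit at least one scheduled 5-minute item, they support the reading of the row but do not prove it. They also leave open which visual analog scale falls at week 42 and which at week 54. That does not affect the week-12 start.

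**What a week-12 rating reflects.** A psilocybin participant with both sessions has had 25 mg/70 kg at week 4 and 25, 30 or 40 mg/70 kg at week 8. The second dose depends on tolerability, willingness and the MEQ score. One rating cannot be divided between the two sessions, and grouping participants by second dose is confounded by the response that set it. The documents do not say how many will have both sessions, so the share affected is unknown.

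**The case against.** The strongest reply is that an Aim 1 outcome need not be acute. Hypothesis 1 also covers tolerability, adverse events belong to Aim 1 and are collected throughout follow-up, and Table 1 groups these scales under Safety. The risk in Section 4.1.3.1.1 is a pattern of misuse, for which weeks 12, 24 and 36 are sensible. Sections 3.1.5 and 4.1.3.1.1 also say that psilocybin is not reliably reinforcing, and nothing in the documents shows that early desire would arise and then fade. This stands as a defence of the later readings. It does not explain why there is no early one.

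Other data cover part of the gap. The TLFB records drug use at weeks 8 and 12, and adverse events are recorded from week 4. Neither asks systematically about desire or craving for the study drug.

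A reader might infer that the ratings cannot be tied to any dose, or that no rating follows the first 25 mg/70 kg session alone. The documents do not support either. Participants whose second session is cancelled have had only that one session by week 12, and those whose dose is held have had only that dose level. Control participants who take the open-label session have one planned psilocybin dose, 25 mg/70 kg, with a rating afterwards. That rating is open-label, and by then the term study medication covers two drugs.

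A reader might also infer that the arm contrast would be falsely reassuring. That does not follow: the randomised comparison at week 12 is valid for week 12. It simply does not speak to the earlier weeks.

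**Conclusion.** The point holds as a gap in timing for one secondary safety outcome. Under Table 1 as best read, the scales have no reading until 8 weeks after the first session and 4 weeks after the second. Early effects on desire and craving are not captured on them, and in participants with both sessions the week-12 value cannot be attributed to a single session. The week-12 to week-36 contrasts remain sound as measures of persistence. The primary outcome is not affected.

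This rests on two assumptions: that the week-12 start in Table 1 is read correctly, which the visit totals support, and that the separate SAP cited in Section 3.3.12 sets no earlier time point. The text of that SAP was not available to me. Whether early desire or craving would occur, and how large it would be, cannot be judged from the documents. This is a cheap improvement, not a threat to the trial's main conclusions.

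**What to change.** Add the abuse-potential scales to the week-5 visit in Table 1, and name week 5 in Sections 3.3.12.2.1 and 3.3.12.2.2 as the Aim 1 time point for the psilocybin versus diphenhydramine contrast. Report weeks 12, 24 and 36 as persistence. Weeks 9 and 39 can be added for short-term follow-up after the later sessions. If only persistence is intended, the minimum change is to relabel the scales as a persisting safety measure and take them out of the acute-effects outcomes.

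The cost is 5 minutes per visit: each of these visits goes from 55 to 60 minutes, or 3 × 5 = 15 minutes per participant if all three are used. All three visits already take place. The schedule amendment needs IRB approval under Section 3.3.14.1.

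Two limits should be written into the plan. At week 5 a second session is already planned for week 8, so the item on using the drug again will partly measure willingness for that session; interpretation should rest on the intoxication and craving items. Readings at weeks 9 and 39 generally reflect cumulative exposure, with second-session doses that depend on earlier response. The added visits therefore do not provide an unconfounded comparison of 25, 30 and 40 mg/70 kg.
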